10.1 Definitions

The following definitions will apply to the reporting of adverse events:

- 1) Serious Adverse Event: Any adverse experience occurring at any dose that is fatal or life threatening; requires in-patient hospitalization or prolongation of an existing hospitalization; is a persistent significant disability/incapacity; is a congenital anomaly or birth defect; or is an important medical event that may not result in death, be life-threatening, or require hospitalization but, based upon appropriate medical judgment, may jeopardize the subject and may require medical or surgical intervention to prevent one of the outcomes listed above.
- 2) Unexpected Adverse Event: Any adverse experience that is not identified in nature, severity, or frequency in the Investigator's Brochure for NTZ.
- 3) Severity of adverse events will be assessed by the Investigator using the Toxicity Grading Scale Tables provided in Appendix II (derived and adapted from "Guidance for Industry: Toxicity Grading Scale for Healthy Adult and Adolescent Volunteers Enrolled in Preventive Vaccine Clinical Trials", US Dept. of HHS, FDA, CDER, September 2007 and the National Institutes of Health, National Cancer Institute Common Terminology Criteria for Adverse Events (CTCAE) version 5.0).
- 4) Causality (relationship to treatment) will be assessed as follows:
 - *Definitely Related*: The adverse event is clearly related to the investigational agent(s) or research intervention: the adverse event has a temporal relationship to the administration of the investigational agent(s) or research intervention, follows a known pattern of response, and no alternative cause is present.
 - *Probably Related*: The adverse event is likely related to the investigational agent(s) or intervention: the adverse event has a temporal relationship to the administration of the investigational agent(s) or research intervention, follows a known or suspected pattern of response, but an alternative cause may be present.
 - *Possibly Related*: There is a reasonable possibility that the event may have been caused by or is linked in a significant way to the research; the adverse event has a temporal relationship to the administration of the investigational agent(s) or research intervention, follows a suspected pattern of response, but an alternative cause is present.
 - *Unrelated (or Not Related)*: The adverse event is clearly NOT related to the investigational agent(s) or intervention: the adverse event has no temporal relationship to the administration of the investigational agent(s) or research intervention, follows no known or suspected pattern of response, and an alternative cause is present.

Under double-blind treatment conditions, it should be assumed that all subjects are taking the test drug.

10.2 Clinical Adverse Events

At the time of each return visit, the subject will be questioned regarding the occurrence and nature of any adverse events. All events must be recorded in the subjects' medical records and in the EDC system. Any subject affected will be examined by the Investigator as deemed necessary to ascertain the course of the event and any residual effects.

All moderate and severe adverse events will be reviewed by the Principal Investigator who will determine using his/her best clinical judgment whether they warrant the subject to be discontinued from the study. The Sponsor will be notified immediately if a subject is discontinued from the study. For all adverse events that require the subject to be discontinued from the study, relevant clinical assessments and laboratory tests will be repeated as clinically indicated until final resolution or stabilization of the event(s).

All subjects will be instructed to contact the Investigator, Investigator's assistants, or clinical personnel should the subject have any serious adverse experiences. Serious adverse events (SAEs), including death regardless of the cause, must be reported to the Sponsor immediately (within 24 hours of the initial report).

A serious event requiring immediate notification by telephone is an event that:

- results in death
- is life threatening
- requires inpatient hospitalization or prolongation of an existing hospitalization
- is a persistent or significant disability/incapacity
- is a congenital anomaly/birth defect
- an important medical event that may not result in death, be life-threatening, or require hospitalization but, based upon appropriate medical judgment, may jeopardize the subject and may require medical or surgical intervention to prevent one of the outcomes listed above.

An overdose is defined as any intentional or unintentional consumption of the drug by any route that exceeds the highest dose stated in the Investigator's Brochure or in an investigational protocol, whichever dose is larger. Overdoses without an associated adverse event should be recorded, but not reported as an adverse event.

10.3 Reporting Requirement

The Principal Investigator is required to notify The Romark Institute for Medical Research (Sponsor) immediately of any unexpected, fatal, or life-threatening experience and all unusual, alarming, or serious reactions to medication regardless of any opinions as to the cause/effect relationship. All SAEs will also be reported to the IRB. Adverse events should be reported to:

The Romark Institute for Medical Research
Medical Affairs

10.4 Medication Modification/Withdrawal Due to an Adverse Event

No dose adjustment is permitted during the 5-day treatment period. If a severe adverse reaction develops during therapy, the study medication should be discontinued, and the subject should be withdrawn from the study.

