5.9 Study Discontinuation

Rules for discontinuation of a patient or for discontinuing the study are provided in section 11.2. All subjects discontinued from the study before day 7 will be evaluated at study discontinuation using the procedures described above for day 7. All subjects discontinued from the study after day 7 will be evaluated at study discontinuation using the procedures described above for day 22.

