8.4.1 Efficacy Analyses

Efficacy analyses will be based on a population consisting of all subjects that received at least one dose of study drug and had laboratory-documented influenza infection (infected intent-to-treat or ITTI population). Laboratory-documented influenza infection is defined by identification of influenza virus in nasopharyngeal secretions by RT-PCR or viral culture at baseline, day 2 or day 3.

There will be one primary efficacy analysis:

- Time to Symptom Response for the NTZ treatment group will be compared to that of the placebo treatment group using a stratified Gehan-Wilcoxon test ($\alpha = 0.05$) stratified by (1) time since symptom onset for each subject at enrollment (≥ 24 hours, $>24 - 36$ hours, >36 hours) and (2) whether the subject received seasonal influenza vaccination after August 1, 2018. Subjects without a Symptom Response being recorded will be treated as censored as of their last diary without a documented Symptom Response.

If the primary analysis is significant at the 0.05 level, a key secondary efficacy analysis will be formally evaluated at the 0.05 level as follows:

- Time to Ability to Perform All Normal Activities for the two treatment groups will be compared using a stratified Gehan-Wilcoxon test ($\alpha = 0.05$) stratified by (1) time since symptom onset for each subject at enrollment (≥ 24 hours, $>24 - 36$ hours, >36 hours) and (2) whether the subject received seasonal influenza vaccination after August 1, 2018. Subjects without an Ability to Perform All Normal Activities response being recorded will be treated as censored as of their last diary without a documented Ability to Perform All Normal Activities response.

If both the primary analysis and the key secondary efficacy analysis are significant at the 0.05 level, another secondary efficacy analysis will be formally evaluated at the 0.05 level as follows:

- Proportions of subjects experiencing one or more complications of influenza including pneumonia, otitis media, bronchitis, sinusitis, worsening of pre-existing health conditions, systemic antibiotic use for infections secondary to influenza infection, hospitalization due to influenza or complications of influenza and death will be compared between the treatment groups using a Fisher's exact test ($\alpha = 0.05$).

A third secondary analysis will be performed as follows:

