11 DISCONTINUATION

11.1 Study Discontinuation:

The study may be discontinued under the following circumstances:

- 1) The Sponsor reserves the right to discontinue the study at any time.
- 2) Adverse event listings will be produced for safety monitoring at least once every two weeks during recruitment. The data will be tested to determine if there are greater than 5% of the subjects who have had \geq grade 3 adverse events considered by the Investigator to be possibly, probably or definitely related to the study drug (defined by the Toxicity Grading Scale Tables provided in Appendix II).

If greater than 5% of the subjects have at least one grade 3 or grade 4 adverse event considered to be possibly, probably or definitely related to the study drug by the study Medical Monitor, then the study must be stopped and the Institutional Review Boards, and FDA's Division of Antiviral Drug Products will be notified. All safety and activity data will be submitted to the FDA in a timely manner.

11.2 Subject Discontinuation:

Treatment will be discontinued for individual subjects for the following reasons:

- 1) An allergic-like reaction occurs or is suspected.
- 2) Medical conditions that may require study discontinuation in the Investigator's judgment.
- 3) Subject desire to discontinue participation.

In the case of an allergic-like reaction or other medical condition requiring subject discontinuation, appropriate treatment will be instituted by the Investigator.

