⁵ Laboratory safety tests include hemoglobin, hematocrit, complete blood count (total and differential), platelet count, random blood sugar, total cholesterol, HDL, LDL, triglycerides, albumin, AST, ALT, GGT, alkaline phosphatase, bilirubin (total/direct), BUN, creatinine, sodium, potassium, chloride and routine urinalysis (glucose, proteins and blood).

⁶ All subjects will maintain an electronic diary until day 22 (+3). Site staff will contact subjects as needed during study to ensure timely completion of electronic diary.

⁷ Collection of unused IMP and completion of pill count log form will be performed at unscheduled visit if applicable.

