10.2.2 Analysis of the Primary Efficacy Parameter

The primary efficacy parameter, time to Symptom Response, will be derived as follows:

Event: Time of Symptom Response – time of the first dose
 Censored: Time of last symptom assessment – time of the first dose

If Symptom Response is achieved at the time of the first symptom assessment diary record, the subject will be excluded from the analysis.

If Symptom Response is not achieved prior to a subject’s last available diary assessment, but the criteria are met at the last available diary assessment with no evidence of symptom relief medication intake during that diary period, time of Symptom Response will be considered to have occurred at the start of the last daily diary period.

Time to Symptom Response for the NTZ treatment group will be compared to that of the placebo treatment group using a Gehan-Wilcoxon test stratified for (1) time from onset of illness to time of first dose of study medication (0-24, >24-≤36, or >36 hours from onset), and (2) vaccination status (Y/N). The comparison will be graphically depicted using Kaplan-Meier curves.

Analysis Population(s):	Confirmed Influenza
Derived Variables:	Event: Time of symptom response – time of the first dose Censored: Time of last symptom assessment – time of the first dose

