10.3 Sensitivity Analyses of the Primary Efficacy Analysis

10.3.1 Sensitivity Analysis Assuming Time of Symptom Response of 21 Days for Discontinued Subjects

Repeat the primary efficacy analysis assuming a time of Symptom Response of 21 days (504 hours from first dose of study medication) for subjects who discontinued the study prior to achieving Symptom Response.

Analysis Population(s):	Confirmed Influenza
Derived Variables:	See Section 10.2: Primary Efficacy Analysis.

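### A severe adverse reaction takes the subject out of the study as well as off the drug, so an observable recovery time is replaced by censoring

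*Protocol*

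**What the plan says.** **Stopping and leaving.** Protocol 10.4 deals with a severe adverse reaction during the 5 days of dosing: "the study medication should be discontinued, and the subject should be withdrawn from the study". Protocol 10.2 covers all moderate and severe adverse events and has the investigator decide "using his/her best clinical judgment whether they warrant the subject to be discontinued from the study". Protocol 11.2 opens with "Treatment will be discontinued for individual subjects for the following reasons" and then lists the subject's wish to end participation among those reasons, so stopping treatment and leaving the study are not kept apart.

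**Follow-up after leaving.** Protocol 5.9 provides one exit evaluation: "All subjects discontinued from the study before day 7 will be evaluated at study discontinuation using the procedures described above for day 7". A later exit uses the Day 22 procedures. Neither list (5.6, 5.7) includes FLU-PRO. Protocol 10.2 adds clinical and laboratory follow-up of the event itself. Footnote 6 of the study schedule has all subjects keep the diary to the Day 22 visit, but does not say whether that includes subjects who have been withdrawn.

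**Analysis.** Protocol 8.4.1 states: "Subjects without a Symptom Response being recorded will be treated as censored as of their last diary without a documented Symptom Response". SAP 10.2.2 sets the censoring point at "Time of last symptom assessment". It counts a response if the criteria are met at the last available diary without relief medication. SAP 10.4.1 has the same structure for Time to Ability to Perform All Normal Activities. SAP 10.3.1 repeats the primary analysis with 504 hours "for subjects who discontinued the study prior to achieving Symptom Response". No such analysis is listed for the key secondary endpoint.

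**The concern.** The outcome that 10.4 gives up could easily be observed: it is a once-daily questionnaire on a device the subject already has. Censoring assumes that the withdrawn subject would have recovered like those still being followed. A severe drug reaction is a doubtful basis for that assumption. Nausea, stomach ache, vomiting and diarrhoea are FLU-PRO items (SAP 10.4.3), so a severe gastrointestinal reaction could be both the reason for withdrawal and an unresolved endpoint symptom.

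The 504-hour rule makes the opposite assumption, very late recovery. If withdrawals concentrate on NTZ, it counts against NTZ. Neither rule uses the real recovery time. For the key secondary endpoint, which is formally tested at 0.05 after a significant primary result, only the censoring assumption is available.

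The rule also sits poorly with the rest of the protocol. Efficacy is analysed in an infected intent-to-treat population (8.4.1), and 9.5 keeps subjects who miss doses or take prohibited medication in the study. A subject with a severe reaction is the one who is sent home.

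**Working it through.** **1. The plan's own figure.** Protocol 8.1 has 552 evaluable subjects and 8% incomplete data: 552 / (1 − 0.08) = 600, as stated. The 552 at 90% power cannot be reproduced, because it used day-by-day curves that are not in the text. The change proposed here does not alter either number.

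**2. Who is affected.** A subject withdrawn under 10.4 who has already responded, or who meets the criteria at the last diary, still counts as an event. All others are censored during days 1 to 5 or so, when few have recovered.

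**3. How many.** Protocol 1.2.7 reports that under 1% stopped therapy for an adverse event. With 300 per arm, 0.01 × 300 = 3, so under 3 per arm.

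**4. Effect on the test.** The Gehan test compares subjects in pairs. A subject censored on day 3 is compared only with those who recovered by then, so a slow recovery on NTZ mostly drops out of the score. To size this, trials were simulated with no true difference. Assumptions:
- 300 per arm, daily assessment, follow-up to 504 hours, unstratified Gehan test
- lognormal recovery with median 170 h and third quartile 290 h, varied from 130/220 to 210/360
- 3 withdrawals on NTZ and none on placebo, last diary on days 2 to 5, not yet recovered
- 40,000 trials per case; standard error √(0.025 × 0.975 / 40,000) ≈ 0.001

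One-sided rate of false results favouring NTZ (nominal 0.025):

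| Handling | Withdrawals from slowest quarter | Random withdrawals |
|---|---|---|
| Censored at last diary | 0.032–0.033 | 0.024–0.027 |
| 504 h assigned | 0.022–0.024 | 0.019–0.021 |

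With all diaries kept the rate was 0.024–0.026. The two-sided rate with censoring was 0.049–0.052. A repeat of the 170/290 case with 8,000 trials gave 0.025 with all diaries kept, 0.031 and 0.026 with censoring (slowest quarter, random), and 0.024 and 0.021 with 504 h.

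**5. Less extreme splits.** Same base case, slow withdrawals censored, 8,000 trials (standard error about 0.002): 1 on NTZ and 0 on placebo gave 0.029 one-sided and 0.050 two-sided. A split of 2 and 1 gave 0.029 and 0.051. With 504 h assigned, the 2 and 1 split gave 0.025 one-sided.

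**6. Different curves.** A separate simulation used placebo medians of 144, 192 and 240 h, with spread set to give about 90% power at 276 per arm for a 40 h difference (2,000 runs per case, standard error √(0.025 × 0.975 / 2,000) ≈ 0.0035). With 300 per arm and no true effect, the rates favouring NTZ when the slowest responders are withdrawn and censored were:

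| NTZ subjects withdrawn | One-sided rate |
|---|---|
| 0.5% | 3.5–4.4% |
| 1% | 3.3–4.4% |
| 2% | 4.8–5.2% |
| 5% | 11–15% |

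Withdrawal unrelated to recovery time left the rate at about 2–3% throughout. The 504 h rule held the slow-responder case at about 1.9–4.0%. The 5% row is far above the historical rate and serves only as an outer bound.

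**The case against.** The case against acting is that nothing has been shown to harm the planned test, which is two-sided. In the first simulation the two-sided rate stays nominal, and only an all-NTZ, all-slow pattern moves the one-sided rate. The documents do not show that severe reactors recover slowly. Influenza symptoms are not adverse events unless caused by the drug (Protocol 10). The excess diarrhoea in RM08-3001 (8.1% against 3.3%) and the chromaturia in RM08-3003 led to no discontinuation. For the primary endpoint, SAP 10.3.1 and the last-diary rule already exist. Sections 10.2 and 10.4 can be read as a general rule and a narrower case. The missing 504-hour analysis for the key secondary endpoint concerns every dropout, not only those under 10.4. Finally, a protocol amendment needs IRB approval (16.3), and version 1.5 is dated January 2019 for a trial expected to end in April 2019.

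Much of this stands. The bias is small, the worst case is assumed, and the 504-hour rule leans against NTZ only when withdrawals concentrate there. The under-1% figure pools several indications, so treating it as an upper limit is an inference. What remains is that an explicit rule discards obtainable outcomes. Footnote 6 does not override it, and the sensitivity analysis replaces one assumption with another. The timing argument applies to the protocol wording; the SAP addition can still be made, since SAP section 6 allows revision before database lock and version 1.2 is not yet dated.

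**Conclusion.** The point holds as a recommended improvement with a small effect. At fewer than 3 affected subjects per arm, the worst case examined in the main simulation raises the one-sided error from about 0.025 to 0.032–0.033. Random withdrawal leaves it essentially unchanged, and the existing 504-hour analysis removes the worst-case inflation for the primary endpoint. The key secondary endpoint has no such check. These figures depend on assumed recovery curves, an assumed split of withdrawals and an unstratified test, so they show a range and do not forecast this trial. The reason to change the rule is that following these subjects costs almost nothing, not that the bias is large.

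**What to change.** **Protocol 10.4.** Keep the stop of study medication. Replace withdrawal from the study with: *the subject continues the eDiary to day 21 and attends the Day 7 and Day 22 visits, unless consent is withdrawn or the investigator judges continued participation unsafe.*

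**Protocol 5.9, 10.2 and 11.2.** Align each so that stopping treatment and leaving the study are separate decisions.

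**SAP.** Keep 10.3.1 for subjects who truly leave. Add the same 504-hour analysis for Time to Ability to Perform All Normal Activities.

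**Cost.** Wording in four protocol sections, through an amendment with IRB approval, and one added sensitivity analysis. No extra patients or procedures are needed. A handful of subjects off drug complete some further diary days and already scheduled visits. If enrolment is too far advanced for an amendment, the SAP addition can be made alone.

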10.5 Medication Errors

A medication error is defined as any preventable event related to dosing instructions, product labeling, or packaging that causes or leads to inappropriate medication use or subject harm while the medication is in the control of the investigative site or subject. Medication errors which result in adverse events should be recorded and reported as adverse events. All other medication errors should be reported to the study Sponsor through the Medical Affairs department within 7 days of identification by the site.

11 DISCONTINUATION

11.1 Study Discontinuation:

The study may be discontinued under the following circumstances:

- 1) The Sponsor reserves the right to discontinue the study at any time.
- 2) Adverse event listings will be produced for safety monitoring at least once every two weeks during recruitment. The data will be tested to determine if there are greater than 5% of the subjects who have had \geq grade 3 adverse events considered by the Investigator to be possibly, probably or definitely related to the study drug (defined by the Toxicity Grading Scale Tables provided in Appendix II).

If greater than 5% of the subjects have at least one grade 3 or grade 4 adverse event considered to be possibly, probably or definitely related to the study drug by the study Medical Monitor, then the study must be stopped and the Institutional Review Boards, and FDA's Division of Antiviral Drug Products will be notified. All safety and activity data will be submitted to the FDA in a timely manner.

11.2 Subject Discontinuation:

Treatment will be discontinued for individual subjects for the following reasons:

- 1) An allergic-like reaction occurs or is suspected.
- 2) Medical conditions that may require study discontinuation in the Investigator's judgment.
- 3) Subject desire to discontinue participation.

In the case of an allergic-like reaction or other medical condition requiring subject discontinuation, appropriate treatment will be instituted by the Investigator.

12 ELECTRONIC DATA COLLECTION (EDC) SYSTEM

An EDC system will be used for this study ([REDACTED]). Prior to study initiation, site staff and authorized Romark personnel will be trained to use this system.

All electronic source forms are to be completely filled out by the examining site staff and reviewed and signed off on by the Investigator(s). Electronic diaries will be completed by the study subjects and reviewed by study personnel and authorized Sponsor representatives.

